Clinical Trial Protocol

Document Number: c37738815-04	
EU CT No.	2022-502264-20-00
BI Trial No.	1397-0016 (CRO-No BID22145-22145X)
BI Investigational Medicinal Products	BI 1291583
Title	A phase I, open-label, single dose, mass balance trial to investigate metabolism and pharmacokinetics of BI 1291583 (C-14) administered as oral solution in healthy male subjects
Lay Title	A study in healthy men to test how BI 1291583 is processed in the body
Clinical Phase	I
Clinical Trial Leader	[REDACTED] [REDACTED],
Investigator	[REDACTED]
Current Version, Date	Version 4.0, 13 Jun 2023
Original Protocol Date	22 Dec 2022
Page 1 of 75	
Proprietary confidential information © 2023 Boehringer Ingelheim International GmbH or one or more of its affiliated companies. All rights reserved. This document may not - in full or in part - be passed on, reproduced, published or otherwise used without prior written permission	

Proprietary confidential information © 2023 Boehringer Ingelheim International GmbH or one or more of its affiliated companies

CLINICAL TRIAL PROTOCOL SYNOPSIS

Company name	Boehringer Ingelheim
Original protocol date	22 December 2022
Revision date	13 June 2023
BI trial number	1397-0016
Title of trial	A phase I, open-label, single dose, mass balance trial to investigate metabolism and pharmacokinetics of BI 1291583 (C-14) administered as oral solution in healthy male subjects
Principal Investigator	[REDACTED]
Trial site	[REDACTED]
Clinical phase	I
Trial rationale	The trial is intended to investigate the basic pharmacokinetics, excretion pathways and metabolism of BI 1291583
Trial objective	
• To assess the mass balance and total recovery of [¹⁴C]-radioactivity in urine and faeces following a single oral dose [REDACTED] BI 1291583 (C-14)• To provide plasma and urine samples for pharmacokinetic investigations• To provide plasma, urine, and faeces samples for metabolic profiling and structural identification of metabolites

Trial endpoints	
Primary endpoints:
 
Primary endpoints will be the mass balance and total recovery of [¹⁴C]-radioactivity in urine and faeces:
 
 • $fe_{urine, 0-tz}$ (fraction of [¹⁴C]-radioactivity excreted in urine expressed as percentage of the administered dose over the time interval from 0 to the last quantifiable time point) • $fe_{faeces, 0-tz}$ (fraction of [¹⁴C]-radioactivity excreted in faeces expressed as percentage of the administered dose over the time interval from 0 to the last quantifiable time point) 
Timeframe: The timeframe for determination of these endpoints depends on individual excretion/recovery of radioactivity and may vary between 2 and 6 weeks, inclusive, after drug administration.
 
Secondary endpoints:
 
The following secondary endpoints will be evaluated for [¹⁴C]-radioactivity, BI 1291583 and five metabolites (M407(1) / BI 1373234, M396(1) / CD 18507, M397(1) / CD 17849, M549(1) / CD 16785 and M141(1) / CD 16426) in plasma:
 
 • C_{max} (maximum measured concentration of the analyte) • AUC_{0-tz} (area under the concentration-time curve of the analyte over the time interval from 0 to the last quantifiable time point)
Trial design	Open-label, non-randomized, single-dose, single-arm, single-period design
Number of subjects	
total entered	8
on each treatment	8
Diagnosis	Not applicable
Main inclusion criteria	Healthy male subjects, age of 18 to 55 years (inclusive), body mass index (BMI) of 18.5 to 29.9 kg/m ² (inclusive)
Test product	BI 1291583 (C-14) as oral solution [REDACTED]
dose	[REDACTED] containing a radioactive dose of approximately ≈ 0.36 MBq (0.04 mSv)
mode of administration	Oral with 240 mL of water after an overnight fast of at least 10 h
Duration of treatment	One day (day 1), single dose of radiolabelled oral solution (Test product)
Statistical methods	Descriptive statistics will be calculated for all endpoints

FLOW CHART

Period	Visit	Day	Planned time (relative to first drug administration) h:min]	Approximate clock time of actual day [h:min]	Event and comment	Safety laboratory ⁷		Blood sampling for PK and total radioactivity ⁸		Blood sampling for metabolic profiling ⁹		Urine sampling ¹⁰		Faeces sampling ¹¹		Vomit collection (if applicable)		12-lead ECG		Vital signs (BP, PR)		Questioning for AEs and concomitant therapy ⁶		
SCR	1	-28 to -2			Screening (SCR) ¹	x ^A												x	x					
	2	-1	-18:00	14:00	Admission to trial site	x ^{B,5,17}								x ¹⁴										
			-14:00	18:00	Light supper (voluntary) ^{3,15}					x														
		1	-1:00	07:00			x ²	x ²									x ²	x ²						
			0:00	08:00	Drug administration		x ^C	x																
			1:00	09:00			x ^C	x																
			1:30	09:30			x ^C	x																
			2:00	10:00	240 mL fluid intake		x ^C	x	x	—														
			3:00	11:00			x ^C	x	x	—														
			4:00	12:00	240 mL fluid intake, thereafter lunch ³		x ^C	x	x	—													x	
			6:00	14:00			x ^C	x	x	—														
			8:00	16:00	Snack ³		x ^C	x	x	—														
			10:00	18:00			x ^C	x	x	—														
			11:00	19:00	Dinner		x ^C	x	x	—														
			12:00	20:00			x ^C	x	x	—														
			13:00	21:00	Snack		x ^C	x	x	—														
			14:00	22:00			x ^C	x	x	—														
		2	24:00	08:00			x ^B	x	x	—	—	—	—	▼			x	x ¹⁸						
		3	48:00	08:00			x ^C	x	x	—	—	—	—											
		4	72:00	08:00			x ^C	x	x	—	—	—	—											
		5	96:00	08:00			x ^C	x	x	—	—	—	—											
		6	120:00	08:00			x ^C	x	x	—	—	—	—											
		7	144:00	08:00			x ^C	x	x	—	—	—	—											
		8	168:00	08:00			x ^C	x	x	—	—	—	—											
		9	192:00	08:00			x ^C	x	x	—	—	—	—											
		10	216:00	08:00			x ^C	x	x	—	—	—	—											
		11	240:00	08:00			x ^C	x	x	—	—	—	—											
		12	264:00	08:00			x ^C	x	x	—	—	—	—											
		13	288:00	08:00			x ^C	x	x	—	—	—	—											
		14	312:00	08:00			x ^C	x	x	—	—	—	—											
		15	336:00	08:00	Breakfast (voluntary), discharge from trial site ^{3,16}	x ^B	x	x	▼	▼							x	x	x ¹⁸					

Proprietary confidential information © 2023 Boehringer Ingelheim International GmbH or one or more of its affiliated companies

Period	Visit	Day	Planned time (relative to first drug administration) h:min]	Approximate clock time of actual day [h:min]	Event and comment	Safety laboratory ⁷	Blood sampling for PK and total radioactivity ⁸	Blood sampling for metabolic profiling ⁹	Urine sampling ¹⁰	Faeces sampling ¹¹	Vomit collection (if applicable)	12-lead ECG	Vital signs (BP, PR)	Questioning for AEs and concomitant therapy ⁶
		20	461:00	13:00	Start home collection					▲				
		21	485:00	13:00	Admission to trial site ^{12,13}	x ¹⁷	x	x	▲	+				
		22	509:00	13:00	Discharge from trial site ^{12,19}				▼	▼				
		27	629:00	13:00	Start home collection					▲				
		28	653:00	13:00	Admission to trial site ^{12,13}	x ¹⁷	x	x	▲	+				
		29	677:00	13:00	Discharge from trial site ^{12, 19}				▼	▼				
		34	797:00	13:00	Start home collection					▲				
		35	821:00	13:00	Admission to trial site ^{12,13}	x ¹⁷	x	x	▲	+				
		36	845:00	13:00	Discharge from trial site ^{12, 19}				▼	▼				
		41	965:00	13:00	Start home collection					▲				
		42	989:00	13:00	Admission to trial site ^{12,13}	x ¹⁷	x	x	▲	+				
		43	1013:00	13:00	Discharge from trial site ^{12, 19}				▼	▼				▼
FU	3	42-50			End of study (EoS) examination ⁴	x ^D						x	x	x

1. Subject must be informed and written informed consent obtained prior to starting any screening procedures. Screening procedures include physical examination, check of vital signs, ECG, safety laboratory (including drug screening), demographics (such as race, and ethnic origin, including determination of body height and weight, smoking status and alcohol history), relevant medical history, concomitant therapy and review of inclusion/exclusion criteria. [REDACTED]
2. The time is approximate; the procedure is to be performed and completed within the 4 h prior to drug administration.
3. If several actions are indicated at the same time, the intake of meals will be the last action.
4. At the end of study (synonym for end of trial), the EoS examination includes physical examination, vital signs, ECG, safety laboratory, recording of AEs and concomitant therapies. [REDACTED]
5. EoS examination to be performed earliest on day 42 with the last blood samples (PK, metabolic profiling) or prior to discharge on Day 43, if all once-weekly 24 h sampling periods are needed. To provide flexibility for EoS appointments, EoS examination is allowed up to day 50.
6. Safety laboratory, serum/urine drug and alcohol screening will be done (see Section 5.2.3). For these activities there is a time window of ± 4 hours.
7. AEs and concomitant therapies will be recorded throughout the trial; during in-house days subjects will be specifically asked for at least twice daily.
7. Safety laboratory sets (A, B, C, D) see Table 5.2.3: 1

Proprietary confidential information © 2023 Boehringer Ingelheim International GmbH or one or more of its affiliated companies

8. Pharmacokinetics (PK): BI 1291583 and its metabolites [REDACTED] in plasma (see Section [5.3.2](#)); [C-14] BI 1291583 total radioactivity in whole blood and plasma (see Section [5.3.2](#)).
[REDACTED]

9. Metabolite sampling times may be adapted based on information obtained during trial conduct (e.g. levels of radioactivity in each urine and/or plasma sample) as long as the overall blood volume stays the same.
[REDACTED]

10. Urine collection intervals (for PK of BI 1291583, and [¹⁴C] -radioactivity assessment and metabolic profiling; planned time): On Day -1 or Day 1 (within 14 hours prior to dosing) pre-dose (blank) spot sample, on Day 1 prior to start of urine collection voiding of the bladder, 0-4, 4-8, 8-12, 12-24, 24-48, 48-72, 72-96, 96-120, 120-144, 144-168, 168-192, 192-216, 216 -240, 240-264, 264-288, 288-312, 312-336 hours after administration of BI 1291583 (C14). Thereafter, if warranted, 24 h collections are to be performed every 7 days starting on Day 21. Urine sampling for PK/[¹⁴C]-radioactivity and metabolic profiling will be stopped when release criteria for radioactivity recovery (see Section [3.1](#)) have been met (earliest stopping on Day 15). “+” means: end of last collection interval, start of following collection interval. For details on sample usage see Section [5.3.2.2](#).
[REDACTED]

11. All stools ([¹⁴C]-radioactivity and metabolic profiling) will be collected quantitatively in portions up to 336 hours (sampling intervals of 0-24, 24-48, 48-72, 72-96, 96-120, 120-144, 144-168, 168-192, 192-216, 216 -240, 240-264, 264-288, 288-312, 312-336 hours after administration of BI 1291583 (C14). Thereafter, if warranted, 24 h collections are to be performed every 7 days starting on Day 20. Further details regarding home collection see footnote 13. For blank sample see footnote 14. Faeces sampling for [¹⁴C]-radioactivity and metabolic profiling will be stopped when release criteria for radioactivity recovery (see Section [3.1](#)) have been met (earliest stopping on Day 15). “+” means: end of last collection interval, start of following collection interval. For details on sample usage see Section [5.3.2.3](#)).
[REDACTED]

12. The planned times for admission, discharge, start and end of the urine and faeces collection intervals are approximate. The procedures are to be performed within a time window of \pm 4 hours to the planned time. However, the ambulatory onsite collections should be at least over 24 hours.

13. Subjects are to collect faeces at home within 24 h intervals before admission to once-weekly in-house collection intervals. Home collection intervals: Day 20-21, 27-28, 34-35, and 41-42. If faeces are collected in the subsequent in-house collection interval, faeces collected at home will be discarded. If no faeces is collected in the subsequent in-house collection interval (no defecation), last faeces collected at home in the 24 h interval before admission be used instead for analysis.

14. Subjects will collect a pre-dose (blank) faeces sample at home or at the site on Days -2 (after screening, if screening is on Day -2), -1 or 1 (prior to dosing) in specific containers provided by [REDACTED]. Only the last pre-dose faeces sample will be analysed (if applicable).

15. Subjects are to be fasted for at least 10 h before drug administration.

16. Prior to discharge from trial site on Day 15 confirmation of fitness will be performed including physical examination, ECG, vital signs, safety laboratory, recording of AEs and concomitant medication.

17. Testing for SARS-CoV-2 (PCR or antigen test) will be performed on Day -1 prior to admission, on Day 2, and at each admission to the trial site for 24-hours visits. Additional tests may be performed as needed based on the current status of the pandemic.

18. [REDACTED]

19. Formal assessment and confirmation of fitness is based on questioning for adverse events and concomitant medication and personal judgement of the investigator.

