3. DESCRIPTION OF DESIGN AND TRIAL POPULATION

3.1 OVERALL TRIAL DESIGN

The trial will be performed as an open-label, single-arm, single-dose trial in healthy male subjects to investigate the basic pharmacokinetics of BI 1291583, its metabolites (M407[1] / BI 1373234, M396(1) / CD 18507, M397(1) / CD 17849, M549(1) / CD 16785 and M141(1) / CD 16426) and [¹⁴C]-radioactivity, including mass balance, excretion pathways and metabolism following a single oral dose of [REDACTED] BI 1291583 (C-14).

A total of 8 healthy male subjects are planned to participate in the trial.

The planned radioactive dose per subject is approximately ≈ 0.36 MBq (0.04 mSv).

On Day 1, subjects will receive the drug product, i.e. [REDACTED] BI 1291583 (C-14) and will then stay in the study centre up to the morning of Day 15 for collection of samples of blood, urine and faeces, and if applicable for collection of vomit (within 24 hours after drug administration).

[REDACTED]

Subjects will be readmitted to the study centre for 24 h collection intervals of urine and faeces on Days 21, 28, 35, and 42, if release criteria have not been met before. Within 24 hours before each of these once-weekly in-house collection intervals, subjects are to collect faeces at home. This 24-h interval home collection faeces will be used for analysis in case no defecation occurs in the subsequent 24 h in-house collection interval. Otherwise it will be discarded.

For determination of whether release criteria have been reached for individual subjects, [¹⁴C]-radioactivity will be measured in excreta (urine, faeces), and vomit, if applicable. The actual recovery results will be reported as a percentage of the administered dose.

If the following release criteria have been met, the subsequent 24 h collection intervals after Day 15 will not be performed:

- Greater than or equal to 90% of the administered [¹⁴C] dose has been recovered in urine and faeces combined over the investigational period

and

- If <1% of the [¹⁴C] dose administered has been collected in urine and faeces within 2 separate, consecutive 24-h intervals

Note:

For calculation of release criteria during clinical conduct the fraction of administered [¹⁴C] dose will be rather underestimated as it will be based on the available samples, only. For the final analysis, the total excreted [¹⁴C]-radioactivity will be derived including an interpolation method to account for the time periods without samples taken (see Section [7.2.2](#)).

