5.3.2.3 Sampling of faeces

Faeces will be collected at time points or in intervals as indicated in the [Flow Chart](#):

- To determine total [¹⁴C]-radioactivity
- To investigate the metabolic profiling of BI 1291583 (to be reported separately)

A blank sample will be taken within approximately 48 hours prior to drug administration. If several samples are available, the sample closest to drug administration will be used for analyses.

Faeces samples collected after administration of BI 1291583 (C-14) until release criteria are met are planned to be used for determination of [¹⁴C]-radioactivity. Samples to be used for metabolic profiling will be selected according to the levels of radioactivity in each faeces sample interval. For faeces samples to be discarded (see footnote 13 and 14).

All stools will be collected continuously in portions up to 336 hours after drug administration. All stool portions will be taken quantitatively at the time-points depicted in the [Flow Chart](#). The weight of the faeces and the exact times of faeces collection will be recorded in the eCRF.

If subjects are to collect faeces during the ambulatory phase of the study (see Section [3.1](#) for release criteria), subjects are to collect faeces at home within 24 h intervals before admission to once-weekly in-house collection intervals. Home collection intervals are (if applicable): Days 20-21, 27-28, 34-35, and 41-42. All faeces samples (including home collection, if

Proprietary confidential information © 2023 Boehringer Ingelheim International GmbH or one or more of its affiliated companies

applicable) will be shipped [REDACTED]. If faeces is collected during in-house collection interval, this faeces sample will be used for analysis and the respective home collection faeces sample has to be discarded. If no faeces is collected in the subsequent in-house collection interval (no defecation), faeces collected at home will be used instead for analysis.

[figure not shown]
For a detailed description of faeces sample preparation, sample storage, labelling, and sample shipment refer to the laboratory manual.

[figure not shown]

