6.2.2 Treatment period

Each subject is expected to participate in one treatment period (Visit 2).

Proprietary confidential information © 2023 Boehringer Ingelheim International GmbH or one or more of its affiliated companies

On Day -1 of the treatment period study participants will be admitted to the trial site and kept under close medical surveillance until discharge from the trial site on Day 15. In the morning of Day 15, the subjects will then be allowed to leave the trial site after formal assessment and confirmation of their fitness.

Until release criteria (see Section [3.1](#)) have been reached, subjects will take part in the 24-h collection intervals of urine and faeces. For these additional 24 h collection intervals, subjects will be admitted to the trial site on Days 21, 28, 35, and 42. One day later, on Days 22, 29, 36, and 43, respectively, subjects will be discharged from the trial site after formal assessment and confirmation of their fitness.

Within 24 h before each once-weekly in-house collection interval, subjects are to collect faeces at home (beginning of home collections on Days 20, 27, 34, and 41). Faeces collected in these 24 h home-collection intervals will be used for analysis in case no defecation occurs in the subsequent 24 h in-house collection interval. E.g., if no defecation occurs in in-house collection interval Day 21-22, faeces of home-collection interval Day 20-21 will be used for analysis. If, however, faeces are collected in the subsequent 24 h in-house collection interval, faeces collected at home will be discarded. Once release criteria are reached, home collections will be stopped.

Irrespective of whether release criteria have been met or not after collection interval Days 42-43, no further collections are planned. For details on time points and procedures for collection of plasma, whole blood, urine and faeces samples for PK analysis and mass balance assessment, refer to [Flow Chart](#) and Section [5.3.2](#).

The safety measurements performed during the treatment period are specified in Section [5.2](#) of this protocol and in the [Flow Chart](#). AEs and concomitant therapy will be assessed continuously from obtaining subject's written informed consent until the end of trial examination. For details on times of all other trial procedures, refer to the [Flow Chart](#).

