7.2.2 Primary endpoint analyses

The primary endpoints (refer to Section [2.1.2](#)) will be calculated according to the relevant BI internal procedures. The analysis will be descriptive in nature. To avoid underestimation of the total recovery of [¹⁴C], the excretion during the non-sampling phase of the study will be estimated using linear interpolation between the observed 24-h sampling periods before and after the non-sampling period for urine and feces respectively.

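### Only empty in-house faeces days are replaced by the previous day's home stool, which biases late faecal recovery (fe_faeces,0-tz) upward on average

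*Protocol*

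**What the plan says.** The rule appears in four places in the protocol.

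- Flow Chart, footnote 13: if the in-house day is empty, "in-house collection interval (no defecation), last faeces collected at home in the 24 h interval before admission be used instead for analysis".
- Section 3.1: "This 24-h interval home collection faeces will be used for analysis in case no defecation occurs in the subsequent 24 h in-house collection interval".
- Section 5.3.2.3: "If no faeces is collected in the subsequent in-house collection interval (no defecation), faeces collected at home will be used instead for analysis". If there is an in-house stool, "this faeces sample will be used for analysis and the respective home collection faeces sample has to be discarded".
- Section 6.2.2: "Faeces collected in these 24 h home-collection intervals will be used for analysis in case no defecation occurs" in the in-house interval that follows.

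For the final analysis, Section 7.2.2 says "the excretion during the non-sampling phase of the study will be estimated using linear interpolation between the observed 24-h sampling periods" before and after each gap, separately for urine and faeces. SAP Section 7.4.1 repeats this without change.

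Neither document gives a 48-h denominator, a time slot for the substituted stool, a flag for substituted visits or a sensitivity analysis. Protocol Sections 7.2.2 and 7.3.2 and SAP Section 6.6 refer to internal procedures that are not shown.

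The substitute is also described in two ways. Footnote 13 limits it to the last home stool; Section 5.3.2.3 does not.

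**The concern.** An empty in-house day is not missing data. It is a true zero, and the retained content leaves with the next stool. Averaged over subject-weeks, in-house amounts with their zeros kept are close to the true daily excretion, because high values after a pause balance the zeros. Footnote 13 removes the zeros and keeps the high values.

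fe_faeces,0-tz is a primary endpoint and total recovery is the first main objective. On average the rule overstates late recovery and shifts the split between routes toward faeces. Section 7.2.2 gives avoiding underestimation as its reason for interpolating, but zeros that are kept do not cause underestimation on average.

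Data from 0 to 336 h, and subjects released at Day 15, are not affected.

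**Working it through.** The plan states no figure for this rule, so there is none to reproduce.

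**1. Direction.** Let A be the in-house amount (0 if there is no stool), H the home amount, and μ the true mean daily faecal excretion. With steady excretion and stool timing unrelated to the visit, E[A] = μ. Under footnote 13,

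E[analysed] = μ + P(A = 0) × E[H | A = 0] ≥ μ.

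If a stool occurs each day independently with probability p, then E[H | A = 0] = μ and the inflation of a weekly value is 1 − p: +10% at p = 0.9, +20% at 0.8, +30% at 0.7. It is nil only if no in-house day is ever empty, or if an empty one never follows a home stool.

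**2. Weight of each weekly value (Flow Chart hours).** The in-house windows are 485–509, 653–677, 821–845 and 989–1013 h, and the gaps before them are 149, 144, 144 and 144 h. Weight = (half gap before + window + half gap after) / 24:

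| Visit | Calculation (h) | Days |
|---|---|---|
| Day 21 | 74.5 + 24 + 72 = 170.5 | 7.1 |
| Day 28 | 72 + 24 + 72 = 168 | 7.0 |
| Day 35 | 72 + 24 + 72 = 168 | 7.0 |
| Day 42 | 72 + 24 = 96 | 4.0 |

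With two visits the weights are 7.1 and 4.0 days. With one visit the weight is (74.5 + 24) / 24 = 4.1 days.

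**3. Hand check of size (assumed: 7-day half-life, 1% of dose per day over 312–336 h).** The home windows are centred at 473, 641, 809 and 977 h, that is 149, 317, 485 and 653 h after 324 h. The rates there are 0.541, 0.270, 0.135 and 0.068% per day. Weight times rate gives 3.84 + 1.89 + 0.95 + 0.27 = 6.95 points. Multiplying by 1 − p gives about 0.7 / 1.4 / 2.1 points at p = 0.9 / 0.8 / 0.7. Stools also carry earlier, higher input, so the exact values are slightly larger.

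**4. Simulation (40,000 subjects per setting, same inputs).** There is one possible stool per day, at about 08:00 (SD 2 h) or at a uniformly random time. Each stool carries all input since the previous one. Truth is the radioactivity in stools from 336 h to the end of the last visit. The share due to the rule is the plan's estimate minus the in-house-only estimate with zeros kept. Only the last home stool is used, as in footnote 13. Results are for p = 0.9 / 0.8 / 0.7.

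| Visits | Timing | % of true late faecal excretion | Points of dose |
|---|---|---|---|
| Four | morning | +8 / +15 / +23 | +0.8 / +1.5 / +2.3 |
| Four | random | +19 / +24 / +30 | +1.8 / +2.3 / +2.9 |
| Two | morning | +7 / +13 / +20 | +0.5 / +1.1 / +1.6 |
| Two | random | +16 / +21 / +25 | +1.3 / +1.6 / +2.0 |
| One | morning | +4 / +9 / +13 | +0.2 / +0.5 / +0.7 |
| One | random | +11 / +14 / +17 | +0.6 / +0.7 / +0.9 |

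The percentages do not depend on the excretion rate; at 0.2% per day the points are one fifth of these. With four visits at 1% per day, a 3-day half-life gives +0.2 to +1.0 points and a 14-day half-life +1.3 to +5.0.

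With morning stools, 33 / 51 / 61% of subjects have at least one substitution over four visits and 18 / 30 / 38% over two. Of substituted subjects, 32–38% still fall below their true excretion, so the bias holds in expectation and not for each subject.

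**5. Alternatives (four visits, 7-day half-life, points of dose).**

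| Estimator | Mean error, morning | Mean error, random | RMSE, morning | RMSE, random |
|---|---|---|---|---|
| Plan | +0.9 / +1.6 / +2.5 | +2.2 / +2.7 / +3.4 | 3.7 / 5.1 / 6.7 | 4.7 / 5.9 / 7.5 |
| Zeros kept | +0.1 to +0.2 | +0.4 | 3.8 / 4.9 / 6.3 | 4.7 / 5.6 / 6.8 |
| Both days pooled over 48 h | 0.0 to +0.1 | +0.3 | 3.0 / 3.8 / 4.7 | 3.2 / 4.0 / 5.0 |

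Pooling lowered RMSE against the plan in every setting run (half-life 3, 7 or 14 days; one, two or four visits), by 15 to 41%.

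**The case against.** The direction is hard to dispute. The case on the other side concerns size and practicality.

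- **The inputs are assumed.** This stands. At 0.2% per day, four visits with morning stools give only about +0.2 to +0.5 points. At p = 0.95 the share is about 4%, and at 0.98 about 2%.
- **Noise exceeds bias.** At p = 0.9 (morning) the per-subject RMSE is 3.7 against a mean error of +0.9. This is true, but averaging over subjects reduces noise and not bias, and pooling reduces both.
- **The time slot is not stated.** If the home stool stayed in its own slot beside a retained in-house zero, the effect would be about half. That reading fits poorly with text that uses the home sample in place of the in-house one.
- **Which home stool counts is unclear.** Counting all home faeces raises the random-time result to about +3.0 / +3.4 / +3.9 points, so the table in step 4 is not an upper limit.
- **Release and the last quantifiable time point were left out of the simulation.** A separate run included them (20-day half-life, p = 0.7, 1% per day, mean Day 15 recovery 90%). The rule's share was 4.36 − 0.72 = 3.6 points with release, and 4.56 − 1.68 = 2.9 with the last quantifiable time point as well. Without either, at mean Day 15 recovery 80%, it was 5.02 − 0.36 = 4.7. The effect is smaller, with the same sign.
- **Home collection is unsupervised.** This is the strongest practical point. If 20% of home stools went unrecorded (p = 0.9, morning), pooling would give a mean error of −0.7 against +0.8 for the plan, although RMSE would still be lower (3.2 against 3.8). The plan already relies on home collection alone when the in-house day is empty.
- **The internal procedures may correct this.** That cannot be excluded, but no procedure can recover a home sample that was discarded.

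**Conclusion.** The concern holds. As written, the plan overstates expected post-336 h faecal excretion in subjects not released at Day 15. The sign follows from the one-sided substitution and does not depend on the simulation inputs.

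The size does depend on them: from a few tenths of a point of dose with near-daily stools and low late excretion, to 2 or 3 points over four visits at 1% per day with a 7-day half-life, and up to 5 points at a 14-day half-life. This should be fixed, because it affects a primary endpoint and the better estimator needs samples that are collected and then thrown away.

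Some upward error is not due to this rule. Straight-line interpolation of a declining curve leaves +0.6 to +0.8 points even with pooling at a 3-day half-life.

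**What to change.** **Protocol, footnote 13 and Sections 3.1, 5.3.2.3 and 6.2.2:** keep and assay faeces from both the home and the in-house interval.

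**Protocol Section 7.2.2 and SAP Section 7.4.1, for faeces after 336 h:** define the rate at each weekly visit as the combined amount in both intervals divided by the actual collection duration, with documented empty days counted as zero. Let this rate fill the whole window of about 48 h (461–509, 629–677, 797–845, 965–1013 h) and interpolate only over the remaining gaps (about 125, 120, 120 and 120 h). Use one interval alone only if the other is documented as not collected. Placing the pooled rate in the old 24-h slot would leave +0.5 to +0.8 points of mean error. Actual durations are needed because footnote 12 says "However, the ambulatory onsite collections should be at least over 24 hours". The stool times exist, since Section 5.3.2.3 says "The weight of the faeces and the exact times of faeces collection will be recorded in the eCRF".

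**Release criteria:** leave the faecal value used for release as it is now, and say so. Reconcile footnote 13 with Section 5.3.2.3 on which home stool counts, because that value still feeds release.

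**If home samples are already gone:** flag substituted visits and add a sensitivity analysis with empty in-house days counted as zero. This removes most of the mean bias but is no more accurate per subject when stools are near-daily (RMSE 3.8 against 3.7 at p = 0.9, morning).

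**Cost:** wording changes, plus assay of samples already collected and shipped: at most 4 intervals × 8 subjects = 32, fewer with earlier release. Visits and release decisions do not change. The price is more reliance on home collection, so empty and missed home intervals must be documented.
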